3.2 Study Population

HIV-infected women age 30 – 65 years old enrolled in care at the FACES- supported HIV clinics in Kisumu County in Kenya.

3.3 Sample Size and Power Calculation

The study sample size is calculated based on the primary objective.

We seek to enroll 400 participants in order to obtain sufficient numbers of women who have CIN2/3, our outcome of interest. Based on prior studies in this population, we anticipate approximately 35% of HPV-positive women (N ~ 140) will have biopsy-proven CIN2/3.²⁴ The study design is a non-inferiority trial using results from the only study using standard cryotherapy in a similar population¹⁹ to establish the non-inferiority boundary. We

will compare the efficacy rate in our study using thermocoagulation to the non-inferiority boundary established using the efficacy rate and lower 95% confidence bound from this cryotherapy treatment publication from a similar population.¹⁹

The efficacy results of cryotherapy in the De Vuyst paper were 77.2% (95% CI: 66.4-85.9%).¹⁹ Using 77.2% with a non-inferiority margin of 10% which is at the limit of the confidence bound and is closest to the null effect.²⁴ Using this margin, the new treatment method is hypothesized to be at least as good as cryotherapy. Based on this non-inferiority margin, a sample size of 140 women with CIN2/3 achieves 90% power in using a one-sided test with a significance level of 0.025. Based on this sample size, power of 90%, and significance of 0.025, the minimal detectable effect size (the actual difference between cryotherapy and thermocoagulation) is 0.0102.

We will leverage the robust HIV-care infrastructure at FACES in which patients are seen at every one to three months, and the presence of an established patient tracing system (including home visits) to reduce loss-to-follow-up. Assuming a 14% loss to follow-up, which would result in a sample size of 120, we are still be powered for our non-inferiority margin of 10% with a minimal detectable effect size of 0.0184, with 80% power and an alpha of 0.025. Sample size and non-inferiority calculations used NCSS PASS software and G-Power software.

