7.1 Primary Objective

To evaluate the efficacy of thermal coagulation for the treatment of HIV-positive, HPV-positive women by assessing rates of HPV persistence and CIN2/3 at 12 months after treatment

Four hundred HIV-positive women with positive HPV testing will undergo colposcopy-directed biopsy for disease ascertainment prior to same-day treatment with thermal coagulation. At 12-months after treatment, all participants will undergo repeat HPV testing for persistence, and those who are HPV-positive will undergo repeat colposcopy, and biopsy as indicated for abnormal results, or random biopsy for 25% of those with normal colposcopy. We will define cure as a normal biopsy result or normal colposcopy among those who do not receive a biopsy.

Statistical Analysis: We will report the proportion of women with no evidence of cervical dysplasia at 12-months (primary outcome) follow-up, including 95% confidence intervals. We will extrapolate the rate of disease among those with normal colposcopy based on the rate of disease among the 25% in this group who will receive biopsy, and this will be incorporated in calculating persistence. We will perform a logistic regression to examine predictors of treatment success, using clinical and demographic variables as predictor variables. We will also report the rate of persistence of HPV at follow-up and compare with rates reported in the literature in this same population. We will compare efficacy rates for clearance of CIN2/3 to historical results following cryotherapy treatment in similar settings. A one-sample exact test will be used to compare the obtained efficacy proportion to that of historical controls.

We will leverage the robust infrastructure of the FACES in which patients are seen every one-to three months, and there is an established patient tracing system (including home visits) to reduce loss-to-follow-up. With a loss-to-follow-up rate of 10%, we will still be powered to answer this objective. Prior studies at this clinic have been able to achieve > 90% follow-up rate.³⁶ While limited by the lack of randomization to cryotherapy versus thermocoagulation, this study will provide pilot results that may enable a future randomized study evaluation of these two treatment methods.

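### The one-sample test takes the historical 77.2% as known, so its 0.025 level covers 'cure rate exceeds 67.2%' but not 'no more than 10 points worse than cryotherapy'

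*Combined protocol and SAP*

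**What the plan says.** Section 3.3 declares a non-inferiority design, "using results from the only study using standard cryotherapy in a similar population" to set the boundary. The investigators "will compare the efficacy rate in our study using thermocoagulation to the non-inferiority boundary established using the efficacy rate and lower 95% confidence bound" of that study. The cited efficacy is 77.2%, with 95% limits 66.4% and 85.9%. The margin is given as "Using 77.2% with a non-inferiority margin of 10% which is at the limit of the confidence bound". The same paragraph adds that, with this margin, "the new treatment method is hypothesized to be at least as good as cryotherapy". On size and error it says that "a sample size of 140 women with CIN2/3 achieves 90% power in using a one-sided test with a significance level of 0.025", and it allows for a fall to 120 women after loss to follow-up.

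Section 7.1 names the analysis: "A one-sample exact test will be used to compare the obtained efficacy proportion to that of historical controls". It acknowledges that treatment is not randomized and describes the results as pilot data for a later randomized study. Section 2.1 frames the hypothesis as similarity to reported cryotherapy rates in this population.

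The historical confidence interval is used once, to justify the size of the margin. It does not enter the test, the significance level or the sample size.

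**The concern.** A one-sample test compares one random proportion with a constant. Here the constant is an estimate from a single study whose interval is almost 20 points wide. The test controls error for the statement that cure exceeds the constant. A statement about cryotherapy also depends on how far the published 77.2% lies from the true cryotherapy rate, and nothing in the plan carries that error.

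At stake is what a pass allows the authors to say. Sections 1.4 and 1.5 expect the data to inform national and WHO guidance. A reader told that non-inferiority was shown at one-sided 0.025 would take 2.5% as the chance of wrongly declaring thermocoagulation within 10 points of cryotherapy. The planned test does not secure that.

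**Working it through.** **Inputs.** From 3.3: 77.2% (66.4-85.9%), margin 10 points, one-sided 0.025, n=140 or 120. From 7.1: one-sample exact test. Assumption: historical sample size, which the documents do not print.

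**1. Historical sample size.** I searched n from 20 to 399 for counts that round to 77.2% and have Clopper-Pearson 95% limits rounding to 66.4% and 85.9%. Only 61/79 fits (66.40% to 85.90%). This assumes that the published interval is Clopper-Pearson. The standard error is then sqrt(0.772 × 0.228 / 79) = 4.7 points. For the new arm at 67.2% and n=140 it is sqrt(0.672 × 0.328 / 140) = 4.0 points, so the benchmark is the less precise of the two.

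**2. The rule as planned.** The boundary is 77.2 - 10 = 67.2%. The pass mark is the smallest r with P(X ≥ r | n, 0.672) ≤ 0.025.
- n=140: r = 106 (75.7%), actual size 0.018.
- n=120: r = 92 (76.7%), actual size 0.015.

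So 0.025 is respected for 'cure rate exceeds 67.2%'. As for the plan's own power figure, exact power at n=140 is 70.3% if true cure is 77.2%, and 79.6% at the stated extra 0.0102, against a stated 90%. That is a separate matter and nothing below depends on it.

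**3. Error for the comparative claim, averaged over the historical study.** Let true cryotherapy cure be c and true thermocoagulation cure be c - 0.10. Sum over h = 0 to 79: Binom(h; 79, c) × P(X ≥ r(h) | n, c - 0.10), where r(h) is the exact pass mark for boundary h/79 - 0.10.
- c = 77.2%: 9.3% at n=140, 8.1% at n=120.
- c from 66.4% to 85.9%: 10.2% down to 7.8% (n=140), 8.9% down to 7.0% (n=120).
- Normal check, 1 - Φ(1.96 × SE_t / sqrt(SE_t² + SE_h²)) at c = 77.2%: 10.4% and 9.4%.

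**4. Error with the boundary held at 67.2%.** P(X ≥ 106 | 140, c - 0.10):

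| True cryotherapy cure | Chance of passing when 10 points worse |
|---|---|
| 66.4% | near 0 |
| 74% | 0.2% |
| 77.2% | 1.8% |
| 80% | 8.1% |
| 82% | 19% |
| 85.9% | 57% |

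At the upper limit, the boundary lies 85.9 - 67.2 = 18.7 points below cryotherapy. At the lower limit, it lies 67.2 - 66.4 = 0.8 points above it.

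**5. What a bare pass shows.** 106/140 - 61/79 = 75.7 - 77.2 = -1.5 points. The Wilson limits are 68.0-82.1% and 66.8-85.1%. Newcombe lower limit: -0.015 - sqrt((0.757 - 0.680)² + (0.851 - 0.772)²) = -0.125. Upper limit: +0.107. The interval crosses -10 points. The smallest count at n=140 whose lower limit clears -10 is 110, and P(X ≥ 110 | 140, 0.772) = 39%.

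**6. Margin and confidence limit.** 77.2 - 66.4 = 10.8 points, so a 10-point margin does not sit at the limit. With 66.4% as the boundary, the pass marks are 105/140 and 91/120, one woman lower in each case.

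**The case against.** The strongest reply is that the rule as written fixes the reference at 77.2%. In the scenario of 77.2% against 67.2%, that rule passes wrongly only 1.8% of the time. The 9.3% arises only when the historical study is redrawn and the boundary moves with it. This is right. A reader might infer that the planned test has a flat 9% error, and the documents do not support that. The 9% is an unconditional average; the risk given the boundary actually set is the table above, and it falls towards zero if the true cryotherapy rate is below 77.2%. What stands is that the true rate is unknown and the 0.025 level does not cover it.

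A second reply is that the margin already uses the confidence bound. It does not help: the 10 points are the tolerated loss, and the same 10 points cannot also absorb error in the reference rate.

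Third, fixed performance goals are common in single-arm studies. Agreed. The test is valid for what it tests, and only the conclusion drawn from it needs to change.

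Fourth, the plan is modest in places. Section 2.1 speaks of reported rates, 3.3 offers parity as a hypothesis, and 7.1 admits the lack of randomization. A reader might infer that the plan promises to announce parity; no section scripts such a conclusion. But 3.3 does call the study a non-inferiority trial, and the caveat in 7.1 concerns design, not the sampling error of the benchmark.

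Finally, one might infer two materially different boundaries. The pass mark moves by one woman, and 10 points is the only margin used, so this is a wording note.

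**Conclusion.** The concern holds in a limited form. The planned test supports 'cure rate exceeds 67.2%' at one-sided 0.025. It does not support 'no more than 10 points worse than cryotherapy' at that level. For the comparative claim, the error averaged over the historical study's sampling is about 9.3% at n=140 and 8.1% at n=120. With the boundary held at 67.2%, it depends on the unknown true cryotherapy rate: 1.8% at 77.2%, 8.1% at 80%, and near 0 or 57% at the ends of the published interval.

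These figures rest on 79 women in the cryotherapy study, inferred from the stated estimate and interval. They cover sampling error only, not differences between the studies in population or outcome ascertainment. The data to be collected are unaffected; what changes is what the trial can conclude from them.

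**What to change.** In 3.3 and 7.1:

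- State one boundary, 67.2%, with its pass mark (106/140, or 92/120 after the planned losses), describe it as a fixed performance goal, and limit the test's conclusion to a cure rate above 67.2%.
- Beside it, report the difference from the cryotherapy study with a two-sample 95% interval (Newcombe or Miettinen-Nurminen). Take the count and denominator from the cited publication, not from the back-calculation here.
- Say that the test level does not cover the sampling error of the benchmark.
- Remove the statement of parity with cryotherapy in 3.3. As a wording note, correct the remark that places the margin at the confidence limit.

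The cost is some text and one extra interval, with no new participants or visits. The downside is a narrower headline conclusion. The supplementary interval will also often cross -10 points even if cure rates are equal: with 61/79 it clears -10 only from 110/140, about a 39% chance at a true cure rate of 77.2%, against 70% for the performance goal. For that reason I propose it as a reported estimate and not as a second hurdle; making it a condition for the non-inferiority wording is a trade-off for the sponsor to decide.

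### The stated 90% power with 140 women is not what the design gives: the planned exact test has about 70% power at equal efficacy and about 80% at the stated 0.0102 advantage

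*Combined protocol and SAP*

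**What the plan says.** Section 3.3 describes a non-inferiority comparison with a fixed historical rate. Cryotherapy efficacy is given as 77.2% (95% CI 66.4% to 85.9%), and the margin is set by "Using 77.2% with a non-inferiority margin of 10% which is at the limit of the confidence bound". The number of evaluable women comes from the statement that "we anticipate approximately 35% of HPV-positive women (N ~ 140) will have biopsy-proven CIN2/3", which is 0.35 × 400 = 140.

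The power claim is that "a sample size of 140 women with CIN2/3 achieves 90% power in using a one-sided test with a significance level of 0.025". The next sentence adds that, at this sample size, power and alpha, "the minimal detectable effect size (the actual difference between cryotherapy and thermocoagulation) is 0.0102". The working hypothesis is that "the new treatment method is hypothesized to be at least as good as cryotherapy".

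After a 14% loss to follow-up (120 women), section 3.3 says that the study is still powered "with a minimal detectable effect size of 0.0184, with 80% power and an alpha of 0.025". Section 7.1 uses a different loss rate: "With a loss-to-follow-up rate of 10%, we will still be powered to answer this objective". It also specifies a one-sample exact test for the comparison of efficacy with historical controls.

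**The concern.** A 10-point margin around a rate near 77%, tested in one arm of 140 at one-sided 0.025, looks too small for 90% power. The two statements in section 3.3 also sit badly together. At the same alpha, 140 women with an effect of 0.0102 are said to give 90% power and 120 women with 0.0184 to give 80%, although the two scenarios carry almost the same information.

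The study is presented as a non-inferiority trial sized on its primary objective, and sections 1.4 and 1.5 expect its results to inform national and WHO guidance. If the real chance of missing non-inferiority with equally effective treatments is three or four times what the plan implies, a missed boundary could be taken as evidence against thermocoagulation when it is mainly a matter of sample size.

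**Working it through.** **Inputs.** From section 3.3: reference efficacy 0.772, margin 0.10, one-sided alpha 0.025, n = 140 (120 after 14% loss), stated effects 0.0102 and 0.0184. From section 7.1: exact one-sample test and 10% loss, so n = 0.90 × 140 = 126. The boundary is p0 = 0.772 − 0.10 = 0.672. The sign of 0.0102 is not stated; it is read here as an advantage, which favours the plan.

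**Exact test.** Take the smallest r with P(X ≥ r | n, p0) ≤ 0.025. Power is then P(X ≥ r | n, p1). At n = 140, P(X ≥ 105) = 0.0283 and P(X ≥ 106) = 0.0180, so r = 106 (75.7% cured).

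| n | r | attained alpha | power at 0.772 | at 0.7822 (+0.0102) | at 0.7904 (+0.0184) |
|---|---|---|---|---|---|
| 140 | 106 | 0.0180 | 70.3% | 79.6% | 85.7% |
| 126 | 96 | 0.0180 | 65.3% | 74.9% | 81.6% |
| 120 | 92 | 0.0154 | 60.5% | 70.5% | 77.6% |

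If 0.0102 were a deficit (true efficacy 0.7618), power at n = 140 would be 59.7%.

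**Trying to reproduce 90% by approximation, n = 140, p0 = 0.672.**

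- Null-variance z: Φ[(p1 − p0 − 1.96·√(p0(1−p0)/n)) / √(p1(1−p1)/n)]. At equality, (0.10 − 1.96 × 0.03968)/0.03546 = 0.627, giving 73.5%. At +0.0102, (0.1102 − 0.0778)/0.03488 = 0.93, giving 82.4%.
- Wald (variance at p1): Φ[(p1 − p0)/√(p1(1−p1)/n) − 1.96]. At equality, 2.820 − 1.96 = 0.860, giving 80.5%. At +0.0102, 3.159 − 1.96 = 1.199, giving 88.5%.
- Arcsine: 75.5% and 83.7%.

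**Boundary at the lower confidence limit, p0 = 0.664.** The exact test gives 76.7% at equality and 84.7% at +0.0102. Wald gives 86.1% and 92.3%. The 86.1% is the highest value at equality under any method tried at one-sided 0.025.

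**Internal consistency.** Power depends mainly on (margin + effect) × √n. For the two statements this is 0.1102 × √140 = 1.304 and 0.1184 × √120 = 1.297. The two scenarios should therefore have nearly equal power, and they do: 82.4% and 82.3% by null-variance z, 88.5% and 89.0% by Wald. The plan assigns them 90% and 80%.

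**Possible source, by inference only.** A null-variance z-test at one-sided 0.05 and 90% power gives detectable effects of 0.0100 (n = 140) and 0.0181 (n = 120), close to the stated 0.0102 and 0.0184. Alpha may have been entered as 0.05.

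**What 90% or 80% would need (exact, p0 = 0.672).** At n = 140, 80% power needs an advantage of 0.0107 (true efficacy 78.3%) and 90% needs 0.0255 (79.8%). At n = 120, 80% needs 0.0214 (79.3%). At equal efficacy, exact power first reaches 90% at 213 women and stays there from 227. Null-variance z needs 213 and Wald 185.

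**The case against.** The strongest reply is that section 3.3 never expressly claims 90% power at equality, because its next sentence ties that power to a true difference of 0.0102. On that reading the shortfall is 79.6% against 90%, about 10 points and not 20. This is a fair reading, but the claim still fails under the planned test. Wald comes close with the 67.2% boundary (88.5%) and exceeds 90% with the 66.4% boundary (92.3%). It is not the planned test, however, and with 120 women at +0.0184 it gives 89.0% or 92.5%, where the plan says 80%. It cannot explain both statements.

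Some of the other objections stand. The 120-woman statement is only slightly optimistic: 80% lies between the exact 77.6% and the null-variance 82.3%. Section 7.1 names no power level or alternative, and with 126 women power is 81.6% at +0.0184, so its assurance fails only at equality (65.3%) or at +0.0102 (74.9%). The loss rates of 14% and 10% can be read as two planning scenarios, so aligning them is tidying. Section 7.1 does not say in so many words that the exact test is run against 67.2%; that follows from reading it with section 3.3. Section 7.1 also calls the results pilot and acknowledges the lack of randomization, which makes a misreading of a failed test less likely but does not correct the stated power.

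**Conclusion.** The concern holds. For the exact test at one-sided 0.025 against 67.2%, 140 women give 70.3% power at equal efficacy and 79.6% at an advantage of 0.0102. The figure of 0.0102 is close to the 80%-power effect (0.0107), not the 90%-power effect (0.0255). The shortfall is about 20 points at equality and 10 on the reading kindest to the plan. After the planned losses, power at equality is 60.5% to 65.3%.

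This assumes that 140 women with CIN2/3 are found, that the boundary is 67.2%, and that the historical rate is treated as fixed, as the plan does. Moving the boundary to 66.4% raises exact power at equality only to 76.7%.

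**What to change.** Keep the sample size and restate section 3.3, for example:

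> With 140 evaluable women, the exact one-sided 0.025 test against 67.2% has 70% power if true efficacy is 77.2%, 80% if it is 78.3% and 90% if it is 79.8%. With 120 evaluable women it has about 60% power at 77.2% and 80% at 79.3%.

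State the rejection rule (at least 106 of 140) and say in section 7.1 that the exact test is against 67.2%. Replace the assurance about loss to follow-up there with a figure: 65% power at equal efficacy with 126 women, or about 60% with 120. Use one loss rate in both sections. Before adopting the text, the sponsor should check the software output for the alpha that was entered.

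The cost is wording only. The stated power becomes less favourable; no participant, test or boundary changes.

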3.4 Study Site

This study will take place at the Family AIDS Care & Education Services (FACES)-supported Ministry of Health (MOH) clinics in Kisumu County in Kenya. At FACES, cervical cancer screening using VIA or HPV testing is offered to sexually active women enrolled in care between 18 and 65 years of age, according to the Kenya Ministry of Health guidelines. Women who screen positive are offered treatment onsite when available or referred to a nearby tertiary center.

3.5 Risks and Benefits

3.5.1 Potential Risks

We anticipate that the potential risks to participants in the study will be minimal. Study subjects may feel discomfort or embarrassment during the pelvic exam. There may be minimal discomfort during self-collection of HPV specimens. Participants may be at risk for psychological or emotional discomfort at different stages of the study if they have a diagnosis of CIN2/3 and learn about the potential risk of cervical cancer. Participants may risk some discomfort and mild spotting after the colposcopy and biopsy. We anticipate that this will be minimal, as exams will be performed by trained clinicians, and thermal coagulation would ablate the biopsied area with the tissue desiccation, hence stopping any bleeding. Other mechanisms to achieve hemostasis at bleeding sites including use of Silver Nitrate sticks will be available to study clinicians. Women who are not eligible for thermocoagulation due to large lesions will be referred to a nearby tertiary facility for further care, per clinic protocol. Following treatment for abnormal screening, women will have vaginal discharge for a few days for which they will be provided anticipatory guidance. During the 12-month follow-up visit, all treated women will have repeat screening with colposcopy and biopsy as needed, as well as repeat HPV-testing with provider collection. Twenty-five percent of women who have normal colposcopy results will have a random biopsy for ascertainment of cure after treatment. This may not have been performed in a routine clinical visit and may be associated with slight discomfort, but the risk to the patient will

be minimized by adequate training of clinicians, and anticipatory guidance provided to the patient. We believe that the benefit of reducing verification bias in performing these biopsies will strengthen the study results and prove a strong case for implementing this treatment method on a large scale.

3.5.2 Protection Against Risks

To reduce the likelihood of participants experiencing psychological discomfort, we will make every effort to create a secure and trustworthy environment. Study staff that counsel participants and carry out examinations will undergo training on culturally sensitive ways to reduce discomfort and embarrassment during the pelvic exam, including providing a private area for women to undress for pelvic exams, providing a clean sheet to cover the woman during exams and obtaining verbal consent prior to each step of the procedure. To assist participants who may experience psychological discomfort when learning of a diagnosis of cervical dysplasia, we will ensure access to experienced counselors who work at FACES. When diagnosed with early-stage cervical cancer during this study will be navigated through the referral process to ensure adequate care by a gynecologist oncologist at the referral facility. All study staff will be thoroughly trained in the study protocol, study procedures, good clinical practices and protection of human subjects prior to starting the study. All exams will be performed gently and, in a way that most minimizes discomfort, bleeding or anxiety in the participants.

